11.3.2.3 OTHER EXPLORATORY EFFECTIVENESS MEASURES

Other exploratory effectiveness measures are discussed in this section. Only descriptive statistics will be provided for these exploratory outcomes.

11.3.2.3.1 MEAN ABSOLUTE DIFFERENCE (MAD) BETWEEN SENSOR AND REFERENCE MEASUREMENTS

$$MAD = \left(\sum |(Glucose)_{\text{SENSOR}} - (Glucose)_{\text{REFERENCE}}| \right) / n$$

11.3.2.3.2 MEAN RELATIVE DIFFERENCE (RD) BETWEEN SENSOR AND REFERENCE MEASUREMENTS

$$\text{Mean RD} = \left(\left(\sum \frac{(Glucose)_{\text{SENSOR}} - (Glucose)_{\text{REFERENCE}}}{(Glucose)_{\text{REFERENCE}}} \right) / n \right) \times 100\%$$

11.3.2.3.3 MEDIAN ABSOLUTE RELATIVE DIFFERENCE (ARD) BETWEEN SENSOR AND REFERENCE MEASUREMENTS

$$\text{Median ARD} = \text{Median} \left(\left(\frac{|(Glucose)_{\text{SENSOR}} - (Glucose)_{\text{REFERENCE}}|}{(Glucose)_{\text{REFERENCE}}} \right)_i \right) \times 100\%, i = 1, 2, \dots, n$$

11.3.2.3.4 MEDIAN ABSOLUTE DIFFERENCE BETWEEN SENSOR AND REFERENCE MEASUREMENTS

$$\text{Median AD} = \text{Median} (|(Glucose)_{\text{SENSOR}} - (Glucose)_{\text{REFERENCE}}|_i), i = 1, 2, \dots, n$$

11.3.2.3.5 MEDIAN RELATIVE DIFFERENCE BETWEEN SENSOR AND REFERENCE MEASUREMENTS

$$\text{Median RD} = \text{Median} \left(\left(\frac{(Glucose)_{\text{SENSOR}} - (Glucose)_{\text{REFERENCE}}}{(Glucose)_{\text{REFERENCE}}} \right)_i \right) \times 100\%, i = 1, 2, \dots, n$$

11.3.2.3.6 SYSTEM AGREEMENT WITH REFERENCE

The Agreement of the CGM System to reference measurements will be assessed by looking at the differences ($\frac{|(\text{Glucose})_{\text{SENSOR}} - (\text{Glucose})_{\text{REFERENCE}}|}{(\text{Glucose})_{\text{REFERENCE}}}$) $\times 100\%$ in intervals of [0 – 15%], [0 – 20%], [0-30%], and [0-40%]. For readings less than or equal to 80 mg/dL, the absolute difference in mg/dL between the two glucose results will be calculated. For values greater than 80 mg/dL, the absolute percent difference (%) from the reference values will be calculated.

11.3.2.4 EFFECTIVENESS MEASURE IN FULL GLUCOSE RANGE AND DIFFERENT GLYCEMIC REGIONS

Mean/median absolute relative difference, mean/median relative difference, mean/median absolute difference when reference $\text{YSI} \leq 70 \text{ mg/dL}$, and Agreement between CGM and YSI glucose will be stratified based on YSI glucose ranges. Similar stratification based on CGM glucose will also be performed. (Tables 6A-6D in APPENDIX 1).

11.3.2.5 CONCURRENCE OF SYSTEM READINGS AND YSI VALUES

Tables for concurrence of system and YSI values will be tabulated (Tables 7A and 7B in APPENDIX 1).

11.3.2.6 STABILITY OF THE SYSTEM THROUGHOUT SENSOR LIFE

For the full 180 day duration of the study, performance of the system overtime will be assessed by visit number (Table 8 in APPENDIX 1).

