4.3.10.2 GUIDELINES FOR DETERMINING WHICH CHALLENGE TO CHOOSE (ALL VISITS)

Subject BG levels and direction of those levels determined using the first three SMBG/YSI readings will inform whether the subject will participate in the hypoglycemia or hyperglycemia challenge on that study day, according to the following table as a guideline:

Glucose level	Challenge*
<180 mg/dL	Hypoglycemia challenge
≥180 mg/dL	Hyperglycemia challenge

*Investigator discretion and patient safety will also be considered in determining appropriate challenge. Additional SMBG can be done to determine the appropriate challenge.

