7.6.2 STOPPING CHALLENGES – NO RE-ATTEMPT IN FUTURE GLUCOSE CHALLENGES

- Subject develops significant nausea, vomiting, abdominal pain, chest pain, or develops ketoacidosis
- The subject is unable to cooperate with oral treatment of hypoglycemia
- The glucose is dropping at a rate that may not respond adequately to oral treatment, and the administration of glucagon is required
- The subject experiences symptoms of neuroglycopenia (e.g. lethargy, disorientation, confusion [disordered processing of information or communication], or inappropriate behavior)

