11.1.4 EXPECTED PAIRED POINTS BY RANGE*

The expected number of paired YSI/sensor points by YSI glucose range are targeted as follows:

	Day 1	Day 7	Day 14	Day 22	Day 30	Day 60	Day 90	Day 120	Day 150	Day 180	Total through 180 days
YSI Range / Min # of subjects	160	80	80	160	160	160	155	140	130	112-120	
40-70 mg/dL	1040	520	520	1040	1040	1040	1008	910	845	728-780	8691-8743
71-299 mg/dL	4400	2200	2200	4400	4400	4400	4263	3850	3575	3976-4260	37664-37948
300-400 mg/dL	1280	640	640	1280	1280	1280	1240	1120	1040	896-960	10696-10760
Total	6720	3360	3360	6720	6720	6720	6510	5880	5460	5600-6000	57050-57450
										Total paired points	57050-57450

*Estimates based on 160 subjects inserted, with challenge type distributed equally

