161-200											
201-250											
251-300											
301-350											
351-400											

Table 8. CGM System Accuracy by Visit Number (Sample Table)

Day Number	Number of Paired CGM-YSI	Mean Absolute Relative Difference (%)	Median Absolute Relative Difference (%)	Percent of CGM System Readings Within				
				Percent 15/15% of Reference	Percent 20/20% of Reference	Percent 30/30% of Reference	Percent 40/40% of Reference	Percent Greater than 40/40% of Reference
Day 1								
Day 7								
Day 14								
Day 22								
Day 30								
Day 60								
Day 90								
Day 120								
Day 150								
Day 180								

Table 10: CGM System between System Precision

Level of Mean Glucose	Mean Difference (Sensor 1 - Sensor 2) (mg/dL)	SD of Difference (mg/dL)	N Pairs
<= 70			
71-180			
> 180			
All			

PARD	
PCV	

Confidential

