6.6.4 Other Effectiveness Endpoints

The means and medians of absolute relative difference, absolute difference and relative difference when the reference measurements (Yellow Springs Instrument analyzer) will be presented.

The agreement between the Sensor and the reference measurements at different ranges of reference measurements and of Sensor measurements will also be presented.

Statistical Analysis Plan		Page 18 of 28
Sponsor Senseonics, Incorporated	Study PROMISE Study: A Prospective, Multicenter Evaluation of Accuracy and Safety of an Implantable Continuous Glucose Sensor Lasting up to 180 Days	Version 3.0

Concurrence of the Sensor and the reference standard (Yellow Springs Instrument analyzer) will be presented as Tables. Performance of the Eversense® 180 CGM System over the study period will be assessed by visit.

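### Stability over sensor life is tabulated by visit with no split by, or standardisation for, glucose range, so a change in challenge mix between visits can imitate or mask sensor drift

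*Protocol*

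**What the plan says.** Protocol 11.3.2.6 states that "performance of the system overtime will be assessed by visit number (Table 8 in APPENDIX 1"), and SAP 6.6.4 that "Performance of the Eversense® 180 CGM System over the study period will be assessed by visit". Protocol Table 8 and SAP Table A.9 share one layout: a row per visit day, with columns for number of pairs, MARD, median ARD, four agreement percentages (15/15% to 40/40%) and the percentage beyond 40/40%. There are no glucose-range rows.

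Glucose-range results are planned elsewhere. Protocol 11.3.2.4 says "Agreement between CGM and YSI glucose will be stratified based on YSI glucose ranges", and SAP 6.9 lists glucose strata computed on all samples. The range tables available (protocol 6B to 6D, SAP A.7.1 to A.7.4) have no visit dimension.

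Three features set the glucose mix at a visit:

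- Challenge type. Under protocol 4.3.10.2, glucose levels and their direction "determined using the first three SMBG/YSI readings will inform whether the subject will participate in the hypoglycemia or hyperglycemia challenge on that study day", with 180 mg/dL as the guide value and room for investigator discretion.
- Exit from challenges. Section 7.6.2 is headed "STOPPING CHALLENGES – NO RE-ATTEMPT IN FUTURE GLUCOSE CHALLENGES"; subjects with the listed events have no later challenge.
- Session length. Visits 3 to 10 sample for 8 hours, and Visit 11 (Day 180) for 10 hours.

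The expected counts in protocol 11.1.4 carry the footnote "Estimates based on 160 subjects inserted, with challenge type distributed equally". No rule enforces that split at any visit.

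**The concern.** The challenges deliberately enrich each session for low or high glucose. If relative error differs between ranges, a visit's overall MARD depends on how many of its sessions were hypoglycemia, hyperglycemia or free-range, as well as on the sensor. Reading down Table 8 then mixes sensor age with case mix: a visit with more hypoglycemia challenges could look like deterioration, and one with fewer could conceal it.

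Accuracy through about 180 days is the effectiveness objective, and this table is where change over time would be seen. The analysis is descriptive with no model, so no later step corrects for mix. The range tables cannot be used to rebuild the adjustment: they are not laid out by visit, and the SAP 6.9 strata use all samples, whereas the primary effectiveness set in SAP 6.2 uses 15-minute values.

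**Working it through.** **1. Reproduce the plan's counts (protocol 11.1.4).** Inputs from protocol 4.3: one sample per 15 minutes; 13 low values over 60 minutes in a hypoglycemia challenge; 16 high values over 75 minutes in a hyperglycemia challenge.

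- An 8-hour session has 8 × 4 + 1 = 33 base samples.
- Hypoglycemia session: 13 low + (33 − 5) = 28 mid, total 41.
- Hyperglycemia session: 16 high + (33 − 6) = 27 mid, total 43.
- At 50:50: 6.5 low, 27.5 mid, 8 high, total 42. Times 160 subjects: 1040, 4400, 1280, as printed.
- Day 180 (41 base samples): 6.5, 35.5, 8, total 50. Times 112: 728, 3976, 896, as printed.
- Subjects at the visits before Day 180 sum to 1225. 1225 × 42 + 112 × 50 = 57050, and with 120 at Day 180, 57450. Both match.

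The planned mix (low/mid/high) is therefore 15.5/65.5/19.0% through Day 150 and 13.0/71.0/16.0% at Day 180. It is constant before Day 180 only because an equal split is assumed.

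**2. Primary-set counts.** With only 15-minute values, a hypoglycemia session gives 5 low + 28 mid and a hyperglycemia session 27 mid + 6 high, each totalling 33. At 50:50 the mix is 7.6/83.3/9.1% (Day 180: 6.1/86.6/7.3%).

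**3. Effect of mix with no drift.** Visit MARD = Σ(pairs in range × range MARD) / total pairs. Range MARDs are assumptions, shown over a range; every subject is taken to have a challenge unless stated.

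Primary set, 70% hypoglycemia challenges: 3.5 low, 27.7 mid, 1.8 high. At 30%: 1.5, 27.3, 4.2. With 15/9/7%:

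- 70%: (3.5 × 15 + 27.7 × 9 + 1.8 × 7) / 33 = 314.4 / 33 = 9.53%
- 30%: (1.5 × 15 + 27.3 × 9 + 4.2 × 7) / 33 = 297.6 / 33 = 9.02%

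All samples, same assumption: 419.4 / 41.6 = 10.08% and 382.6 / 42.4 = 9.02%.

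| Assumed low/mid/high | 70% to 30%, 15-minute set | 70% to 30%, all samples |
|---|---|---|
| 12/9/8% | −0.25 | −0.53 |
| 15/9/7% | −0.51 | −1.06 |
| 20/10/7% | −0.82 | −1.71 |
| 9/9/9% | 0 | 0 |

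**4. Chance imbalance.** Assume each subject falls to either challenge independently with probability 0.5, and 160 subjects at each of two visits. The 95% limit for the difference in hypoglycemia share is 1.96 × √(2 × 0.25 / 160) = 0.11. Scaling step 3 by 11/40 gives 0.07, 0.14 and 0.23 points in the 15-minute set, and 0.15, 0.29 and 0.47 on all samples.

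**5. Minor drivers, over 12/9/8% to 20/10/7%.**

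- Day 180 session length at 50:50: −0.03 to −0.09 (15-minute set), −0.04 to −0.16 (all samples).
- Permanent exit of 10 to 30% of subjects, assumed equal across challenge types: −0.01 to −0.15 (15-minute set), −0.02 to −0.25 (all samples).

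**6. Check of the remedy.** With weights fixed at the planned all-visit mix (15.2/66.0/18.7%), visit MARD stays at 9.27, 9.54 and 10.96% under the three unequal assumptions, whatever the visit's own mix.

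**The case against.** The strongest reply is that the by-visit table is richer than one MARD and the likely distortion is small. Much of this stands.

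- A reader might infer that stability rests on a single MARD per visit. It does not: median ARD and five agreement columns sit beside it, and protocol 11.3.2.3.6 scores agreement in mg/dL at or below 80 mg/dL, which softens its dependence on low-glucose relative error. None of these columns is split by range, however.
- Nothing in the documents makes the split move with sensor age. The same guideline covers all visits, and Visits 4 to 11 share an approximate morning timetable. The 70-to-30 swing is an illustration; chance alone gives the smaller figures in step 4.
- A reader might compare a visit of only hypoglycemia challenges with one of only hyperglycemia challenges and quote a shift of two points or more. With 112 to 160 subjects per visit that is not a realistic case.
- A reader might infer from 7.6.2 that free-range sessions must accumulate at later visits. Barred subjects may also leave the study, and section 4.3.4 excludes some subjects from a challenge only for an event in the past 30 days. Low and high shares also fall together on exit and partly cancel, so a systematic hiding of late deterioration is not shown.
- A reader might take the switch to mg/dL at low glucose as the plan's admission that relative error differs there. The documents give no reason for it.
- The text does not say that the range tables are pooled over all visits, and analyses after Visit 8 and after Visit 12 are foreseen. Range tables for each would give two broad periods, not a by-visit view. Some appendix pages were not available, but the row and column layouts of Tables 8 and A.9 were.

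The study is descriptive and has no stability threshold, so no formal decision is at risk. What remains is that the table meant to show stability cannot separate mix from drift.

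**Conclusion.** The point holds as a limit on interpretation. Stability is assessed by visit only, on columns that ignore glucose range, while the mix at each visit is left to arrival glucose and discretion. Challenge split is the material driver; permanent exits and the longer Day 180 session are minor. In the primary set, distortion is about 0.1 to 0.2 points for a chance imbalance and about 0.25 to 0.8 for a large swing; on all samples the effects are roughly double. These sizes rest on assumed range MARDs, an assumed split and, for the chance figure, independence between visits. If range MARDs are equal the effect vanishes, and the added table would show that. The documents do not support a claim that drift will be hidden, or that the bias has a known direction. The pooled MARD through 180 days, which is the effectiveness measure, is not challenged here. The change is worth making because it is cheap and makes the stability statement readable.

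**What to change.** In protocol 11.3.2.6 and SAP 6.6.4, extend Tables 8 and A.9 with:

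- (a) by-visit MARD and agreement within YSI strata, for example ≤70, 71-299 and ≥300 mg/dL;
- (b) a by-visit MARD standardised to one fixed range mix, such as the all-visit mix, on the primary 15-minute set and again on all samples;
- (c) the number of hypoglycemia, hyperglycemia and free-range sessions at each visit.

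State that conclusions on stability are read from (a) and (b) alongside the crude values. The cost is SAP wording and one more table from data already collected; some visit-by-range cells will be small, so show their counts. Challenge and stopping rules are unchanged.

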11.3.2.7 SENSOR PRECISION ANALYSIS

Sensor precision will be evaluated by paired absolute relative difference (PARD) and percent coefficient of variation (PCV). PARD is the absolute value of the Primary Sensor reading minus the paired Secondary Sensor reading divided by the average of the two Sensor readings. PCV is the standard deviation of the two paired Sensor readings divided by the average of the two paired Sensor readings. The mean values of PARD and PCV will be tabulated (Table 10 in APPENDIX 2).

$$\text{PARD} = \left(\left(\sum \frac{|(\text{Glucose})_{\text{SENSOR 1}} - (\text{Glucose})_{\text{SENSOR 2}}|}{(\text{Mean Glucose})_{\text{SENSOR 1 and 2}}} \right) / n \right) \times 100\%$$

$$\text{PCV} = \left(\left(\sum \frac{\text{SD of } (\text{Glucose})_{\text{SENSOR 1}} \text{ and } (\text{Glucose})_{\text{SENSOR 2}}}{(\text{Mean Glucose})_{\text{SENSOR 1 and 2}}} \right) / n \right) \times 100\%$$

11.3.2.8 CALIBRATION FREQUENCY ANALYSIS

After the conduct of the study, additional effectiveness analyses will be performed with a modified calibration scheme to support 1 calibration per day after Day 21 following Sensor insertion (i.e., calibration will be performed twice (2) per day for Days 1-21, followed by once (1) per day for Days 22 until the end of Sensor life). It is important to note that the raw clinical data that is collected by the Sensor is independent of the calibration values that are entered into the MMA. Performing the effectiveness analyses after the collection of Sensor data is analogous to how the effectiveness analyses were performed to demonstrate the accuracy of the algorithm change that was included in Software 602 (SW602), which was approved in the Eversense CGM System PMA (P160048). A separate statistical analysis plan will be developed for this analysis to evaluate the new calibration frequency.

12 DEVICE ACCOUNTABILITY

Only an approved Investigator and investigational site may receive and use the Eversense® 180 CGM System. The product will be packaged and labeled to clearly indicate that it is for clinical investigational use only, and the investigational device must only be used in subjects enrolled in this investigation. The Investigator is responsible for investigational product accountability, reconciliation, and record maintenance. The accountability includes storage of the investigational supplies in a secured location according to the conditions set forth for the device on the label. The investigator must maintain investigational product accountability records throughout the course of the investigation including receipt, use, and final disposition of investigational inventory. The accountability includes documenting the part number, lot number, serial number (and expiration date for sterile components) of investigational device (as applicable) assigned to each subject.

All investigational product (used or not used) must be returned to Senseonics unless otherwise instructed by Senseonics. Explanted Sensors will also be returned to Senseonics using Biohazard Return instructions and supplies.

13 ETHICAL AND REGULATORY CONSIDERATIONS

13.1 STATEMENT OF COMPLIANCE AND GOOD CLINICAL PRACTICE

This clinical investigation will be conducted in compliance with the principles that have their origin in the Declaration of Helsinki (Revision 6, 2008), this clinical investigation plan, requirements of the approving IRB or EC, US Code of Federal Regulations applicable to

clinical studies, ICH GCP E6, ISO 14155 and other applicable regulatory requirements.

This clinical investigation will not be initiated until approval has been obtained from the FDA or local regulating authority as well as IRB/ EC. No deviation from the protocol will be implemented without the prior review and approval of the Sponsor and /or IRB except where it may be necessary to eliminate an immediate hazard to a subject. In such case, the deviation will be reported to the IRB and Sponsor per their reporting requirements.

13.2 INFORMED CONSENT AND INVESTIGATIONAL REVIEW BOARD

The Investigator is responsible for assuring that informed consent is obtained from each subject or (legally authorized representative) prior to participation in the clinical investigation, according to the local clinical site's IRB and applicable regulatory requirements.

The Investigator will prepare an informed consent form (ICF) in accordance with this protocol and applicable regulatory requirements. Prior to the start of the study or revision to study, the informed consent form will be reviewed by the Sponsor for consistency with protocol, and then must be submitted to and approved by the IRB. A copy of the final IRB approved consent form and notification of approval of the clinical protocol must be received and approved by the Sponsor prior to start of study or revision to study. Timely approvals for the continuation of the trial as well as the informed consent form at each clinical site must also be forwarded to the Sponsor.

While an Investigator may discuss general availability of the investigation with a prospective subject without first obtaining consent, informed consent must be obtained from a subject prior to initiation of any clinical procedures dictated by the protocol (e.g., pregnancy testing) that are performed solely for the purpose of determining eligibility to participate in the clinical investigation.

The informed consent process includes both verbal and written explanation. Subjects must be fully counseled and informed of their options, risks and benefits, and have every opportunity to ask questions about participation in the investigation. Insurance coverage will be explained to the subject. This process includes a thorough explanation of the informed consent document that the subject will be asked to sign acknowledging that they understand and desire to participate in the investigation. The subject will be provided a copy of the signed informed consent form. The original ICF remains at the investigational site.

If new information regarding the investigational device becomes available and/or the protocol changes and this information can significantly affect a subject's future health and medical care, subjects will be informed of the information and may be asked to sign a revised informed consent form.

The Investigator will notify the Sponsor within 5 working days, a withdrawal of approval by the reviewing IRB of the investigator's part of an investigation.

13.3 PAYMENT FOR PARTICIPANTS

Subjects will be compensated for their time and travel expenses as detailed in the Informed Consent document.

13.4 AMENDMENTS TO THE PROTOCOL

Investigators may not modify this protocol without obtaining written concurrence of the sponsor and approval by the IRB and required regulatory authorities.

13.5 SPONSOR RESPONSIBILITIES

As the Sponsor of this clinical trial, Senseonics Incorporated has the overall responsibility for the conduct of the clinical trial, including assurance that the study meets the regulatory requirements of the appropriate regulatory bodies. In this study, the Sponsor will have certain direct responsibilities and may delegate other responsibilities to another organization such as a Contract Research Organization (CRO).

The Sponsor will submit all reports required by the appropriate regulatory authorities, including unanticipated adverse device effects, withdrawal of IRB approval, current investigators list, annual progress reports, final report, and protocol violations.

The Sponsor will select the qualified Investigators who will conduct clinical investigations of medical devices under 21 CFR Part 812 and applicable local and regulations.

The Sponsor will maintain copies of correspondence, all data, device shipment records, adverse events, device accountability, and required study documentation as required by the appropriate regulatory authorities.

13.6 INVESTIGATOR RESPONSIBILITIES AND DELEGATION OF STUDY SPECIFIC TASKS

The Investigators commit themselves to conducting the investigation in accordance with the Clinical Trial Agreement, Protocol, and applicable FDA and local regulations for patient safety and control of investigational devices. Investigators are responsible for

submitting and obtaining initial and continuing review of the clinical trial at least annually unless otherwise directed by the IRB and completing all required reports.

Study-specific tasks may be delegated by an Investigator to individuals who are qualified by education, training, and experience. However, the Principal Investigator remains responsible for the conduct of the clinical trial.

A Delegation of Authority Log will be maintained to document the study personnel and their roles and delegated tasks. No study-specific tasks may be performed prior to the appropriate training and completion of the Delegation of Authority Log.

Records to be maintained by the Investigator include, but are not limited to: clinical trial investigational plan and all amendments, signed clinical study agreement, signed financial disclosure forms, IRB communication including approvals and informed consent forms, IRB membership list, correspondence related to the trial, curriculum vitae, delegation of authority documentation, sponsor sign-in documentation, laboratory certification and normal ranges, reports (including annual reports, final reports). For each subject enrolled: signed informed consent form(s), all completed case report forms with source documentation supporting the data, and supporting documentation related to any complication or adverse event.

